## 1 INTRODUCTION

This Statistical Analysis Plan describes the planned analyses and reporting for the clinical trial protocol CD1-NASH-01 version 7.0 dated June 14, 2021 sponsored by CytoDyn Inc. The main objective of this plan is to provide details pertaining to statistical methodology, data conventions, and processes used for the analysis of data from this trial.

This Statistical Analysis Plan provides sufficient detail to meet the regulatory and statistical professional guidelines [1-6].

## 2 PROTOCOL DESIGN AND OBJECTIVES

### 2.1 Study Objectives

Primary Objective:

- The Primary objective of this study is to assess the efficacy of Leronlimab (PRO 140) in improving liver function in adult patients diagnosed with NASH compared to placebo

Secondary Objective:

- The Secondary objective of this study is to assess the safety and tolerability of Leronlimab (PRO 140) in adult patients diagnosed with NASH compared to placebo

### 2.2 Study Design

This is a phase II, multi-center, two-part study.

[figure not shown]
- Part 1. Randomized, double-blind, placebo-controlled, two-arm with 60 patients designed to evaluate the safety, tolerability, and efficacy of leronlimab (PRO 140 700mg dose) or placebo weekly administered subcutaneously (SC) in patients with NASH for 13 weeks.
- Part 2. Non-randomized, single-arm, open-label with 30 patients designed to evaluate the safety, tolerability, and efficacy of leronlimab (PRO 140 350mg dose) weekly administered subcutaneously (SC) in patients with NASH for 13 weeks SC in patients with NASH for 13 weeks

For Part 1 of the study leronlimab 700mg group will be compared to placebo.

For Part 2 of the study leronlimab 350mg group will be compared to placebo from Part 1.

[figure not shown]
The study schematic is presented in Figure 2.1 and Figure 2.2

Figure 2.1: Study Schematic

	STATISTICAL ANALYSIS PLAN (SAP)		
	CD1-NASH-01	Protocol No. CD1-NASH-01	Revision No. Rev. 00

Figure 2.2

See Section 3.3 in the protocol for eligibility and exclusion.

Subjects who complete the treatment period will continue to End of Treatment (EOT) Visit assessments at week 14 and enter the Follow-up Phase of the study. Subjects who meet any criteria for discontinuation of study treatment as specified in Section 5.1 of the protocol, will undergo Early Termination (ET) Visit assessments 7 days after the last injection and enter the Follow-up Phase of the study.

A Follow-up visit will be conducted 28 ( $\pm$  3) days after the End of Treatment (EOT) or Early Termination (ET) Visit.

See Table 4-2 of the protocol for detailed study schedule.

## 2.3 Study Duration

The total Study Duration is up to 22 weeks:

- Screening Period: Up to 4 weeks
- Treatment Period: Up to 14 weeks
- Follow-Up Period: Up to 4 weeks after End of Treatment (EOT) or Early Termination (ET) Visit

## 2.4 Study Centers

Up to 20 centers in the United States (US).

	STATISTICAL ANALYSIS PLAN (SAP)		
	CD1-NASH-01	Protocol No. CD1-NASH-01	Revision No. Rev. 00

## 2.5 Study Target Population

Adult patients with NASH who meet the eligibility criteria will be enrolled.

	STATISTICAL ANALYSIS PLAN (SAP) CD1-NASH-01		
	Protocol No. CD1-NASH-01	Revision No. Rev. 00	Effective Date: 17-Dec-2021

## 2.6 Study Treatments

In Part 1 of study leronlimab 700mg or placebo will be subcutaneously administered every week by a licensed healthcare professional at the study site for 13 weeks.

### Part 1 Treatment Groups

STUDY DRUG	DOSE	ROUTE	SCHEDULE
Leronlimab	700mg	SC	Start on Day 1 and every week thereafter
Placebo	N/A	SC	Start on Day 1 and every week thereafter

In Part 2 of the study, the non-randomized, single-arm, open-label phase, leronlimab 350mg dose) will be administered subcutaneously (SC) weekly for 13 weeks.

### Part 2 Treatment Groups

STUDY DRUG	DOSE	ROUTE	SCHEDULE
Leronlimab	350 mg	SC	Start on Day 1 and every week thereafter

## 2.7 Randomization

Part 1:

Subjects who are eligible to participate in the trial will be randomized 1:1 to one of the treatment groups via IWRS (Interactive Web Based Randomization System) at the Visit prior to IP administration. The randomization will be central and will use 1:1 ratio of Treatment groups

- Leronlimab 700mg SC weekly injection
- Placebo 0mg SC weekly injection

Part 2:

Randomization is not applicable for the open-label, single-arm portion (Part 2) of the study.

## 2.8 Blinding

All subjects, investigators and their staff, and all Sponsor/CRO personnel involved in the management of the study will be blinded to treatment assignments.

Treatment unblinding for the study will occur after all clinical data have been received, data inconsistencies have been resolved, and the database is locked, except for safety reasons on a case-by-case basis (i.e., emergency unblinding).

Note: Blinding is not applicable for the open-label, single-arm portion (Part 2) of the study.

	STATISTICAL ANALYSIS PLAN (SAP) CD1-NASH-01		
	Protocol No. CD1-NASH-01	Revision No. Rev. 00	Effective Date: 17-Dec-2021

## 2.9 Protocol Deviations

The protocol deviations will be classified as minor and major deviations before unblinding.

### 2.9.1 Major Protocol Deviations

The following deviations will be considered as major protocol deviation: and will result in exclusion from PP analysis set:

- Dietary noncompliance clinically significant as deemed per investigator
- Noncompliance with amount of alcohol use as stipulated in exclusion criteria during the study
- Poor diabetic control with consistent elevated fasting blood glucose  $\geq 200$
- Noncompliance with diabetic and or lipid lowering medications clinically significant as deemed per investigator
- Use of Hepatotoxic medications clinically significant as deemed per investigator: including but not limited to: Isoniazid, glucocorticoids- prednisone, NSAIDS, Paracetamol, Ketoconazole, Hydralazine, Iproniazid.
- Missing 2 consecutive doses of IP or less than 80% cumulative compliance
- Not meeting inclusion or exclusion criteria
- Early termination before 14-week evaluation period
- T1 labs meeting exclusion criteria including but not limited to HbA1C  $> 9$ , abnormal TSH and panel, autoimmune disorder with associated hepatitis. Elevations of CRP at T1 should be considered as potential autoimmune etiology until proven otherwise if workup was not performed prior to screening.

## 3 STUDY ENDPOINTS

### 3.1 Primary Endpoint

The primary endpoint for Part 1 of the study is:

Change from baseline in hepatic fat fraction assessed by magnetic resonance imaging-derived proton density fat fraction (MRI-PDFF) at week 14.

### 3.2 Secondary Endpoints

The secondary endpoints for Part 1 of the study are

- Change from baseline in fibro-inflammatory activity as assessed by cT1 (corrected T1) assessed by multiparametric magnetic resonance imaging (MRI) of liver at week 14 (Note: cT1 measured in milliseconds is a quantitative metric for assessing a composite of liver inflammation and fibrosis) fibrosis).
- Change from baseline in liver fibrosis using FibroTest at week 14
- Change from baseline in hepatic inflammatory activity using FibroTest at week 14
- Change from baseline in serum pro-inflammatory biomarkers assessments
- Change from baseline in Gamma-glutamyltransferase (GGT) at week 14
- Change from baseline in Cytokeratin 18 (CK-18) level at week 14
- Change from baseline in Leronlimab (PRO 140) PK assessments

	STATISTICAL ANALYSIS PLAN (SAP) CD1-NASH-01		
	Protocol No. CD1-NASH-01	Revision No. Rev. 00	Effective Date: 17-Dec-2021

The secondary endpoints for Part 2 of the study are:

- Change from baseline in fibro-inflammatory activity as assessed by cT1 (corrected T1) assessed by multiparametric magnetic resonance imaging (MRI) of liver at week 14 (Note: cT1 measured in milliseconds is a quantitative metric for assessing a composite of liver inflammation and fibrosis) compared to part 1 placebo
- Change from baseline in liver fibrosis using FibroTest at week 14 compared to Part 1 placebo
- Change from baseline in hepatic inflammatory activity using FibroTest at week 14 compared to Part 1 placebo
- Change from baseline in serum pro-inflammatory biomarkers assessments compared to Part 1 placebo
- Change from baseline in Gamma-glutamyltransferase (GGT) at week 14 compared to Part 1 placebo
- Change from baseline in Cytokeratin 18 (CK-18) level at week 14 compared to Part 1 placebo
- Change from baseline in Leronlimab (PRO 140) PK assessments compared to Part 1 placebo

### 3.3 Exploratory Endpoints

The exploratory endpoints for Part 1 of the study are

- The fibrosis scores categorized by degree of liver fibrosis as per cT1 value:
  - Mild 800-850 cT1
  - Moderate 851-999 cT1
  - Mild-Moderate 800-999 cT1
  - Severe  $\geq 1000$  cT1
- Change from baseline in Alanine transaminase (ALT) at week 14
- Change from baseline in Aspartate transaminase (AST) at week 14
- Change from baseline in total bilirubin at week 14
- Change from baseline in triglycerides at week 14
- Change from baseline in Low Density Lipoprotein (LDL) at week 14
- Change from baseline in High Density Lipoprotein (HDL) at week 14
- To explore Monocyte/T cell CCR5 biomarkers that may predict activity of leronlimab.

### 3.4 Safety Endpoints

Safety endpoints of the study are:

- Adverse events (AEs)
- Laboratory parameters (blood tests, urinalysis)
- Vital signs (blood pressure, heart rate)
- Subject's medical condition (physical examination including weight)
- Tolerability of repeated subcutaneous administration of Leronlimab (PRO 140) will be assessed by
  - Subject rated 11-point Numeric Pain Rating Scale
  - Investigator-evaluation of injection site reactions.

	STATISTICAL ANALYSIS PLAN (SAP) CD1-NASH-01		
	Protocol No. CD1-NASH-01	Revision No. Rev. 00	Effective Date: 17-Dec-2021

## 4 SAMPLE SIZE

The sample size of 90 total subjects [60 subjects (30 subjects per arm) for the Randomized Phase and up to 30 subjects for the non-randomized, open-label phase] is based on clinical judgment. The number of subjects is deemed adequate to provide clinically meaningful descriptive results consistent with study objectives.

## 5 INTERIM ANALYSIS

No interim analysis (IA) will be performed.

## 6 PRIMARY HYPOTHESIS TO BE TESTED

The null hypothesis of no between treatment group difference in mean change from baseline to Week 14 in Proton Density Fat Fraction (MRI-PDFF) will be tested against the alternate hypothesis of a non-zero difference.

## 7 ANALYSIS SETS

### 7.1 Full Analysis Set

Full analysis set (FAS) will be the set of subjects which is as complete as possible and as close as possible to the intention-to-treat ideal of including all randomized subjects. The FAS is defined as the set of subjects who

- Receive at least one dose of study treatment
- Have at least one post-baseline efficacy assessment
- Subjects who fail to satisfy an entry criterion may be excluded from FAS only under the following circumstances: The entry criterion was measured prior to randomization, the detection of the relevant eligibility violations was made completely objectively, all subjects receive equal scrutiny for eligibility violations and all detected violations of the particular entry criterion are excluded.

The FAS will be used as the primary analysis set.

The randomized treatment will be used for primary efficacy analysis.

### 7.2 Per Protocol Set

The PP set will be used as the supportive analysis set.

The Per Protocol (PP) population is defined as the set of subjects who meet the intention to treat requirements, were not associated with any major protocol violations and have at least 80% compliance with study treatment. This population will be identified before the database lock.

Per protocol set (PP) will be subset of the subjects in the full analysis set who were not associated with any major protocol violations and have at least 80% compliance with study

	STATISTICAL ANALYSIS PLAN (SAP) CD1-NASH-01		
	Protocol No. CD1-NASH-01	Revision No. Rev. 00	Effective Date: 17-Dec-2021

treatment. Subjects will be excluded from the PP if a major protocol deviation occurred. The criteria for major protocol deviations are listed in Section entitled Protocol Deviations.

The actual treatment will be used for the Per Protocol efficacy analysis.

### 7.3 Safety Analysis Set

The Safety Analysis set will comprise all subjects who have received one dose of study treatment. This analysis set will be used for the analysis of safety variables.

Actual treatment received will be used for safety analysis in event of a major protocol deviation.

## 8 DATA HANDLING CONVENTIONS

### 8.1.1 Data entry errors and potential outliers

Patients may have potential outliers for particular observations. Potential outliers based on correct values will be included in the analysis. However, sensitivity analyses excluding outliers may be calculated to evaluate the influence of such extreme values. Values found to be incorrect due to data entry error will be excluded from all analyses as missing values. Incidence of incorrect values and potential outliers may be listed and summarized per treatment arm. If assumptions or data structure do not allow planned analyses, analyses will be updated appropriately.

### 8.1.2 Missing data

Subjects may have missing specific data points for a variety of causes. In general, data may be missing due to a missed visit, non-evaluability of a specific clinical measurement at its planned clinical visit or a subject's early withdrawal from study. All data will be used as observed, and no imputations will be made for any missing data point.

### 8.1.3 Partial dates

Partially incomplete dates will be imputed for dates related to events and follow up information. Dates with missing months or years will not be imputed. Derived data from these dates will be calculated using only the information that is available.

Imputation will be done as described in the following table:

	MISSING	IMPUTE	DURATION CALCULATION
Date	Day	15	Duration will be presented in days and is calculated as the difference between date1 and date2
Date	Month	NONE	Duration will be presented in years and is calculated as the difference between year1 and year2. Example: Duration of NASH diagnosis

	STATISTICAL ANALYSIS PLAN (SAP) CD1-NASH-01		
	Protocol No. CD1-NASH-01	Revision No. Rev. 00	Effective Date: 17-Dec-2021

#### 8.1.4 Derived data

BMI : Body Mass Index is the weight in kilograms divided by the square of height in meters

BMI category: Based upon the calculated value of BMI, patients will be categorized into the subcategories

- Underweight : <18.5
- Healthy weight : 18.5 – 24.9
- Overweight : 25.0 – 29.9
- Low risk obesity : 30.0 – 34.9
- Moderate risk obesity : 35.0 – 39.9
- High risk obesity : >=40.0

Heart rate: the measurements will be categorized as

- Slow: <60 beats per minute
- Normal : 60-100 beats per minute
- Fast :>100 beats per minute

Blood pressure: To evaluate blood pressure results of systolic and diastolic measurements are combined to denote hypertension

- Hypertension: Systolic>=140 and Diastolic>=90
- No hypertension : All other combinations

Duration of NASH diagnosis: Time period in years between date of initial NASH diagnosis and randomization date in the study

Grade change from baseline to week 14 in CT1 by degree of fibrosis

- In patients with CT1 800-849 msec mild
- In patients with CT1 850-999 msec moderate
- In patients with CT1  $\geq$  1000 msec severe

End of Treatment (EOT): Subjects who complete the treatment period of 13 weeks have reached their End of Treatment.

Early Termination (ET): Subjects who meet any criteria for discontinuation of study treatment, as specified in Section 5.1 of the protocol, will undergo Early Termination (ET).

Medications:

- Concomitant medications will be coded using WHO dictionary and associated with ATC levels 1 and 2:

Adverse Events:

- Treatment Emergent AE's (TEAE) are defined as events with an onset on or after the first treatment.

	STATISTICAL ANALYSIS PLAN (SAP) CD1-NASH-01		
	Protocol No. CD1-NASH-01	Revision No. Rev. 00	Effective Date: 17-Dec-2021

- System Organ Class (SOC) and preferred terms (PT) will be associated with each adverse event using most recent version of Medical Dictionary for Regulatory Activities (MedDRA).

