8.3 SAMPLE SIZE DETERMINATION AND RATIONALE

The sample size of 90 total subjects [60 subjects (30 subjects per arm) for the Randomized Phase and up to 30 subjects for the non-randomized, open-label phase] is selected on the basis of clinical judgment and not based on statistical power calculation. The number of subjects is deemed adequate to provide clinically meaningful descriptive results consistent with study objectives.

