### 9.1.6 Demographic and Baseline Disease Characteristics

Demographics and baseline disease characteristics medical history, prior and concomitant medications/therapies will be summarized by treatment group

The following variables will be summarized descriptively using frequency counts and/or summary statistics n, mean, sd, median, min and max, as appropriate:

VARIABLE	TYPE	PRESENTATION
Age	CONT	In years
Gender	CAT	Male vs Female
Racial categories	CAT	Non-Hispanic Caucasian Hispanic Black/African American Asian Natives Other

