## STATISTICAL ANALYSIS PLAN (SAP) CD1-NASH-01

Protocol No. CD1-NASH-01      Revision No. Rev. 00      Effective Date: 17-Dec-2021

BMI	CONT	Continuous
BMI category	CAT	Underweight : <18.5 Healthy weight : 18.5 – 24.9 Overweight : 25.0 – 29.9 Low risk obesity : 30.0 – 34.9 Moderate risk obesity : 35.0 – 39.9 High risk obesity : >=40.0
Blood pressure	CAT	Hypertension: Systolic>=140 and Diastolic>=90 No hypertension : All other combinations
Heart rate	CAT	Slow : <60 beats per minute Normal : 60-100 beats per minute Fast :>100 beats per minute
Alcohol consumption	CAT	Never/Current/Former
Duration NASH diagnosis	CONT	Duration in years
Nash medication	CAT	None/unknown/yes
Stage Liver Fibrosis histology	CAT	F0/F1/F2/F3/F4/Unknown
Stage Steatosis histology	CAT	S0/S1/S2/S3
Stage Steatosis CAP US	CAT	S1 238-260 S2 260-290 S3 >290
Stage Fibrosis US	CAT	F0-F1 2-7 F2 7.5 -10 F3 10 – 14 F4 >14
cT1	CONT	
PDFF	CONT	
Co-morbidities	CAT	Yes/No
Number of co-morbidities	CAT	0-5 5-10 10-15 15-20 20-25 >25
Concomitant medication	CAT	Yes/No
Number of concomitant medications	CAT	0-5 5-10 >10

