#### Subject Listing of Vital Signs

Treatment	Inv.	Subj.	Age(y)/ Sex/ Race	Visit	Systolic BP (mmHg)	Diastolic BP (mmHg)	Vital Sign 3 (units)
Part 1      Placebo	xx	xx	23/ Male/ White	xx xx xx	xx H xx xx	xx L xx xx H	x H xx H xx

The vital signs at every assessed time point and changes from baseline will be summarised using the minimum set of summary statistics n, mean, SD, Median, min and max.

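### The SAP counts a subject as hypertensive only if both pressures are raised, so subjects above one cut-off are tabulated as not hypertensive and the baseline count is too low

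*SAP*

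**What the plan says.** SAP 8.1.4 (Derived data) introduces the variable by saying that "results of systolic and diastolic measurements are combined to denote hypertension". It then gives two categories. The first is "Hypertension: Systolic>=140 and Diastolic>=90". The second is "No hypertension : All other combinations".

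The baseline characteristics table in SAP 9.1.6 carries the same definition under the row for blood pressure: "Hypertension: Systolic>=140 and Diastolic>=90 No hypertension : All other combinations". The two places agree, so a programmer working from either would build the same variable.

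The variable is descriptive. SAP 9.1.6 introduces its table with "The following variables will be summarized descriptively using frequency counts and/or summary statistics n, mean, sd, median, min and max, as appropriate". In that table BMI appears both as a continuous variable and as categories, but blood pressure appears only as this two-level category. Continuous pressures are reported in SAP 9.3.5: "The vital signs at every assessed time point and changes from baseline will be summarised using the minimum set of summary statistics".

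**The concern.** The rule joins the two cut-offs with 'and', and the second category takes every reading that does not meet both. It therefore mixes two kinds of subject: those below both cut-offs, and those at or above exactly one. The label says that neither kind has hypertension, although the second kind is at or above a value that the SAP itself chose as a cut-off. The derivation is fully stated, but its output does not match its label.

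What is at stake is how the study population is described. The table covers the two randomised groups and also the non-randomised 350 mg group, which SAP 2.2 and 9.2 compare with the Part 1 placebo group. A reader who uses the row to see how common raised pressure was, or how alike those groups were, gets a figure that omits every subject with a single raised pressure.

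**Working it through.** **No plan figure to reproduce.** Neither document states a blood pressure mean, standard deviation, correlation or expected prevalence. Group size comes from SAP 4, "The sample size of 90 total subjects [60 subjects (30 subjects per arm) for the Randomized Phase", with up to 30 more in Part 2. Protocol 8.3 says that the total "is selected on the basis of clinical judgment and not based on statistical power calculation", so the sample size supplies no distributional input either.

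**Step 1: what follows from the rule alone.** Let S be systolic >=140 and D be diastolic >=90.

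| Reading | S | D | SAP category | Either-pressure category |
|---|---|---|---|---|
| 145/95 | yes | yes | hypertension | hypertension |
| 180/85 | yes | no | no hypertension | hypertension |
| 135/110 | no | yes | no hypertension | hypertension |
| 130/80 | no | no | no hypertension | no hypertension |

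The SAP counts P(S and D). An either-pressure rule counts P(S or D) = P(S) + P(D) - P(S and D). The second is never smaller than the first, and it is larger whenever at least one subject is above only one cut-off. The direction needs no assumption about the data.

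**Step 2: size, under assumptions.** Take the two pressures as bivariate normal. None of these inputs comes from the documents:

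- systolic mean 125, 130 or 135, with SD 12, 15 or 18;
- diastolic mean 76, 80 or 84, with SD 8, 10 or 12;
- correlation 0.4, 0.5, 0.6, 0.7 or 0.8.

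That is 3 x 3 x 3 x 3 x 5 = 405 scenarios.

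Central case (systolic 130, SD 15; diastolic 80, SD 10; correlation 0.6):

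- P(S) = P(Z >= (140 - 130)/15) = P(Z >= 0.667) = 0.252
- P(D) = P(Z >= (90 - 80)/10) = P(Z >= 1) = 0.159
- P(S and D) = 0.097, from the bivariate normal
- P(S or D) = 0.252 + 0.159 - 0.097 = 0.314
- ratio 3.2 (computed before rounding); in a group of 30, 2.9 against 9.4 subjects

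Selected cases (mean systolic/diastolic, with SDs and correlation r):

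| Assumption | Both | Either | Ratio | Of 30 |
|---|---|---|---|---|
| 125/76, SD 15/10, r 0.6 | 4.5% | 19.5% | 4.4 | 1.3 vs 5.8 |
| 130/80, SD 15/10, r 0.6 | 9.7% | 31.4% | 3.2 | 2.9 vs 9.4 |
| 130/80, SD 15/10, r 0.8 | 12.5% | 28.7% | 2.3 | 3.7 vs 8.6 |
| 135/84, SD 15/10, r 0.7 | 20.3% | 44.1% | 2.2 | 6.1 vs 13.2 |
| Lowest ratio: 135/84, SD 15/12, r 0.8 | 24.2% | 43.6% | 1.8 | 7.3 vs 13.1 |
| Highest ratio: 135/76, SD 18/8, r 0.4 | 2.9% | 40.1% | 13.6 | 0.9 vs 12.0 |

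Over all 405 scenarios the median ratio is 3.6 and the 5th to 95th percentiles run from 2.1 to 9.3. The ratio is at least 2 in 97% of scenarios and at least 3 in 67%. These are shares of an assumed grid, not probabilities.

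**Step 3: will every group be affected?** In the central case 31.4% - 9.7% = 21.7% of subjects are above exactly one cut-off. The chance that a group of 30 contains none is (1 - 0.217)^30, or less than 0.001. Under these assumptions some undercount in each group is close to certain.

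**Step 4: where the variable is used.** It appears in SAP 8.1.4 and in the 9.1.6 baseline table. It is not an eligibility criterion (Protocol 3.3), an endpoint (SAP 3) or an efficacy covariate (SAP 9.1.2, which names only baseline values). The vital-signs tables in SAP 9.3.5 use the continuous measurements.

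**The case against.** The best defence has four parts.

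- **The rule is explicit, exhaustive and consistent.** This is true. The two places do not contradict each other, and the documents give no other definition of hypertension. What remains is internal: a label of no hypertension is attached to subjects above one of the SAP's own cut-offs. That supports changing the rule or changing the label, and it does not make 'or' the only acceptable repair.
- **The information appears elsewhere.** This is also true. Pressures are listed by subject and summarised by visit for all three groups (SAP 9.3.5), and medical history and concomitant medications are summarised by group (9.1.8 and 9.1.9). These outputs let a careful reader see around the row, but they do not correct it, and the baseline table has no continuous blood pressure row beside it.
- **The size is assumed.** This stands. A reader might infer that the row is known to undercount severalfold. The documents contain nothing to establish that; in about a third of the scenarios the ratio is below 3, and its lowest value is 1.8.
- **The row is minor.** This stands. A reader might infer that the table is the plan's main check on whether the 350 mg group resembles the placebo group, or that the efficacy comparison is distorted. No section gives the table that role, and the category enters no model.

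Two further inferences should be resisted. The row is not a prevalence of hypertension under either rule: it classifies measured pressures, so a subject controlled on treatment falls in the lower category both ways. Nor does the rule always hide an imbalance. If one group averaged 128/78 and another 135/82 (SD 15/10, r 0.5), the SAP rule would show 6.0% against 13.8%, a gap of 7.8 points, and an either-pressure rule 26.7% against 44.3%, a gap of 17.6 points. As a ratio, though, the SAP rule shows the larger contrast (2.3 against 1.7).

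**Conclusion.** The point holds as a defect in one descriptive row. By the rule itself, subjects above only one cut-off are reported as not hypertensive, so the baseline count of raised blood pressure is too low in any group that contains such a subject; in practice this is likely to be all three. The row's label is the standard for calling the count too low, since the documents do not define hypertension otherwise.

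The size is conditional. On the assumed distributions an either-pressure rule gives about 2 to 9 times as many subjects (5th to 95th percentile of the scenarios; full range 1.8 to 13.6), with a central case of about 3 against 9 in a group of 30. The documents can neither confirm nor narrow that range.

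The primary endpoint, the ANCOVA, the significance level, the sample size and the safety analyses are untouched. This is a low-priority correction.

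**What to change.** Amend SAP 8.1.4 and the blood pressure row of the table in SAP 9.1.6 together. Either:

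- replace 'and' with 'or', so that a subject is in the hypertension category if systolic is >=140 or diastolic is >=90, and in the other category only if both are below the cut-offs; or
- if the sponsor confirms that the conjunction is intended, keep the rule and rename the categories 'both SBP>=140 and DBP>=90' and 'not both'.

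The change concerns a reporting category only and has no bearing on the management of any subject. It costs one word, or two labels, in two places, plus the matching line of the derivation program and table shell. It needs no new data and should be made before database lock.
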